Before lymphodepletion and 3 days before IMC 002 infusion, if the investigator judges that the subject has significant abnormalities; or the investigator judges that the subject has rapid disease progression compare to the screening time; or the investigator assesses that the patient has significant organ dysfunction (such as severe heart disease, uncontrollable hypertension or diabetes, severe liver or kidney damage, pulmonary edema, severe lung infection, brain metastasis); and it is not suitable for follow-up test procedures, then the lymphodepletion cannot be continued or should be delayed; the CAR T cells should not be infused or the infusion should be delayed.

If the infusion of cells is delayed for more than 5 days after lymphodepletion for any reason, the infusion is not allowed or needs to be delayed.

Withdrawal criteria:

- Subjects may withdraw from the study at any time of their choice.
- Subjects who did not complete the study protocol, including cell infusion and follow-up assessments, are considered to have terminated the study early.
- The reason for termination must be recorded in the CRF and maintained for the specified period of time as required by GCP.
- Subjects may be withdrawn from the study at any time during the study at the discretion of the investigator for reasons of subject safety, behavior, or management reasons, including:
 - 1) Disease progression confirmed by imaging and iRECIST criteria.

- 2) The cumulative treatment reached 96 weeks (no radiographic progression).
- 3) The subjects experienced serious adverse reactions.
- 4) Subject died.
- 5) Subject is pregnant.
- 6) Major protocol deviation included, but not limited to:
 - a) Mistaken for failing to meet inclusion/exclusion criteria
 - b) Concomitant use of prohibited drugs in this protocol
 - c) The subjects did not cooperate with the treatment and follow-up, are lost to the follow-up, or the subjects did not come to the hospital for more than two follow-up visits on time.
- 7) The disease progressed rapidly before the cell infusion, and the investigators determined that other treatment regimens needed to be used based on the maximum benefit of the subjects.
- 8) In the absence of efficacy, the investigator determined that the subject did not benefit from the trial treatment, and continued participation in the study may put the patient at unacceptable risk.

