Secondary endpoints: Engraftment endpoints after infusion of IMC002 (CLDN 18.2 CAR-T cells), i.e., copy number and sustained survival time of cells in vivo.

The “engraftment endpoint” is defined as the number of copies of CLDN 18.2 CAR-T DNA in peripheral blood detected by q-PCR at each visit point from the end of the infusion until any 2 consecutive test results are negative or below the detection limit. The time from the day of infusion to the first negative result or below the lower limit of detection is recorded as the survival time of IMC002 (CLDN 18.2 CAR-T cells).

Safety endpoints: The incidence of DLT is assessed according to NCI CTCAE 5.0 and its correlation with investigational product, lymphodepletion and leukopheresis.

Other safety endpoints:

- The type, incidence, and severity of adverse events, including abnormal clinically significant laboratory test results, abnormal physical examination and blood test results, bone marrow test results, and immunogenicity results after treatment. AE/SAE is assessed according to NCI CTCAE version 5.0. The association of adverse events with the IMC002 CAR-T treatment regimen will be assessed by the investigator according to the attribution evaluation criteria specified by the protocol.
- Grade 3-4 laboratory tests and their association with investigational products, lymphodepletion, and leukopheresis.

Efficacy evaluation endpoints:

Efficacy is evaluated using RECIST1.1 and iRECIST1.1. For each subject, the same technique must be used to obtain tumor imaging during the trial. For subjects first determined to be in complete remission (CR) or partial remission (PR), the assessment results should be confirmed by repeat imaging scans at least 4 weeks later.

Efficacy endpoints include tumor objective response rate (ORR), disease control rate (DCR), duration of response (DOR), progression-free survival (PFS), and overall survival (OS).

Objective response rate (ORR) is defined as the proportion of subjects with confirmed response as CR or PR; tumor response status is assessed by investigators according to Response Evaluation Criteria in Solid Tumors (RECIST1.1).

Duration of response (DOR) interval from first assessment as CR or PR to first assessment as PD or death from any cause (percentage of subjects with DOR ≥ 24 weeks, ≥ 36 weeks, ≥ 48 weeks will be reported).

Disease control rate (DCR) percentage of patients who confirmed as CR or PR or SD (RECIST1.1).

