Descriptive statistical analysis is performed on the indicators, and median Tmax, Cmax, as well as the survival rate and cell number of CAR-T cells in peripheral blood within 96 weeks after IMC002 infusion are provided. The relevant parameters should be analyzed separately for responders and non-responders and compared. Descriptive statistical analysis is performed on the cytokine dose-response relationship, and the median peak value of each cytokine within 4 weeks of CAR-T cell infusion, and the median time to return to baseline or normal range are provided.

The differences in the dose-response relationship of patients in different dose groups are compared.

Ethics:

The protocol (including the informed consent form) must be approved by an independent ethics committee before start. This study strictly follows the protocol and GCP to fully protect the legitimate rights and interests and safety of the subjects.

Research period: Expected from December 2021 to December 2024

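### The responder versus non-responder comparison of 96-week CAR-T persistence can favour responders through follow-up alone, because survival time is defined only for subjects with an observed negative q-PCR

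*Protocol*

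**What the plan says.** The Protocol, under Statistical analysis of dose-response relationship, opens with: "Descriptive statistical analysis is performed on the indicators, and median Tmax, Cmax". It adds the "survival rate and cell number of CAR-T cells in peripheral blood within 96 weeks after IMC002 infusion" and then directs: "The relevant parameters should be analyzed separately for responders and non-responders and compared". No time-to-event method is named for persistence.

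The endpoint is defined under Secondary endpoints. q-PCR is run "at each visit point from the end of the infusion until any 2 consecutive test results are negative or below the detection limit". Then: "The time from the day of infusion to the first negative result or below the lower limit of detection is recorded as the survival time". Nothing is said about a subject whose last sample is still positive. For PFS and OS, by contrast, the protocol gives end dates for subjects without an event.

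Withdrawal criteria state: "Subjects may be withdrawn from the study at any time during the study at the discretion of the investigator". The listed reasons include "Disease progression confirmed by imaging and iRECIST criteria" (item 1), death (item 4) and absence of efficacy (item 8). Subjects without radiographic progression can stay to week 96 (item 2). Under Efficacy evaluation endpoints, a first CR or PR must be confirmed by a repeat scan at least 4 weeks later.

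**The concern.** The comparison groups are formed by an outcome that becomes known only after infusion and that is linked to time on study. The protocol evaluates response after 4 weeks and confirms it at least 4 weeks later, so a confirmed responder has about 8 weeks of follow-up or more. A non-responder has no such minimum and can leave for reasons tied directly to lack of response.

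A subject who leaves while still positive has no survival time under the definition. If only observed negatives are summarised, the group with shorter follow-up contributes mainly early negatives. If the last sample is instead taken as the end of persistence, departure counts as loss of cells. Both routes shorten apparent persistence in non-responders.

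In a study of 10 to 30 subjects, a finding that cells persist longer in responders would be readily believed. A duration summary as now defined could not separate it from length of follow-up.

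**Working it through.** The protocol gives no expected persistence, exit time or group difference, so there is no figure of its own to reproduce. The times below are assumptions. True persistence is set equal in both groups throughout.

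**1. Closed form.** Let persistence and time to leaving be independent and exponential, with medians m_true and m_exit and rates λ = ln 2 / m_true and μ = ln 2 / m_exit. The density of a negative observed at time t is λ·exp(−(λ+μ)t). Dividing by the probability of observing it, λ/(λ+μ), gives (λ+μ)·exp(−(λ+μ)t). Hence

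- median among observed negatives = 1 / (1/m_true + 1/m_exit);
- share of subjects with an observed negative = m_exit / (m_true + m_exit).

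The median is the same if the last sample is counted as the end of persistence, so both readings of the definition give the same result here.

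| True median | Exit median | Observed median | Share with a survival time |
|---|---|---|---|
| 12 wk | 8 wk (non-responders) | 96/20 = 4.8 wk | 8/20 = 40% |
| 12 wk | 30 wk (responders) | 360/42 = 8.6 wk | 30/42 = 71% |
| 24 wk | 8 wk (non-responders) | 192/32 = 6.0 wk | 8/32 = 25% |
| 24 wk | 30 wk (responders) | 720/54 = 13.3 wk | 30/54 = 56% |

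The week-96 limit is ignored. At most 2^(−96/13.3) = 0.7% of subjects would reach it under observation.

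**2. Simulation with visits and minimum follow-up.** Assumptions:
- exponential persistence, median 8, 12, 24 or 36 weeks;
- median time on sampling 24 or 32 weeks in responders (minimum 8) and 8 or 12 weeks in non-responders (minimum 4), in the pairs 32/8, 24/8 and 32/12;
- visits at weeks 1, 2 and 4, then every 4 weeks to 48 and every 8 weeks to 96;
- 12 responders and 18 non-responders (30 is the protocol's upper limit), with 2,000 trials per setting and medians from 100,000 per group.

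The yardstick is how often a two-sided 0.05 test flags a difference that does not exist.

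| Summary | True median 12 wk, sampling 32 vs 8 wk | False positives, same setting | Range over 12 unequal settings |
|---|---|---|---|
| Last sample taken as end | medians 12 vs 4 wk | 65% | 20–94% |
| Observed negatives only | medians 12 vs 4 wk | 26% | 6–28% |
| Kaplan-Meier / log-rank, censored at last sample | medians 12 vs 16 wk | 5.6% | 4.0–5.8% |

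Wherever the first two summaries gave different medians, the difference favoured responders. In one setting (true median 8 weeks, sampling 32 vs 12 weeks) both groups showed 8 weeks on the visit grid. Kaplan-Meier medians agreed to within one visit interval.

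With equal sampling (32 weeks in both groups), false positives were 4.0–5.8% for last sample as end and 3.6–4.5% for observed negatives only. The artefact therefore comes from unequal follow-up.

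**3. Percentages at a visit.** In the same 12-week setting, the true share detectable at week 24 is 2^(−24/12) = 25%. Among subjects sampled at that visit it is 25.3% vs 26.8%. With all infused subjects in the denominator and unsampled subjects counted as negative, it is 15.9% vs 0.8%.

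**The case against.** The protocol does not stop q-PCR at progression. Its sampling rule runs to two consecutive negatives whatever the response, and the explicit stop at progression under Tumor efficacy evaluation is written for imaging and tumor markers. Withdrawal is at the investigator's discretion. This stands: a reader might infer that a spurious difference is certain, but the text supports only that it can arise. Earlier loss of samples remains possible through the withdrawal items, and death ends sampling under any rule. Eligibility asks for an expected survival of only 12 weeks, against a 96-week window.

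Survival rate may mean a visit-wise percentage, and the Statistical Analysis section leaves missing values out of percentages. On that reading there is little artefact (step 3). This also stands, and confines the problem to duration summaries. The protocol nevertheless defines survival time as a duration.

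The exponential exit times fit the protocol loosely. A median of 8 weeks puts 1 − 2^(−4/8) = 29% of non-responder exits before week 4. A median of 30 weeks puts 1 − 2^(−8/30) = 17% of responders off study before confirmation is possible. That is fair, and is why the second check imposes minimum follow-up; the direction is the same.

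Censoring is commonly left to a statistical analysis plan, which is not shown and may supply it. However, the protocol itself fixes both the comparison and a duration definition that omits subjects who leave while positive.

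Finally, a reader might infer that persistence against efficacy is a stated secondary objective. It is not: secondary objective 2 links efficacy to pharmacodynamic biomarkers, and expansion and persistence to those biomarkers and to adverse events.

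**Conclusion.** The point holds in a limited form. Taken together, the survival-time definition, the withdrawal criteria and the planned comparison allow a duration summary to favour responders under equal true persistence. The condition is that sampling ends earlier in non-responders and the summary ignores censoring.

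The sizes (4.8 vs 8.6 weeks, or 6.0 vs 13.3 weeks) illustrate stated assumptions and do not estimate the bias in this trial. The direction was stable over the range tried, while the false-positive rate for observed negatives ranged from near nominal (6%) to 28%.

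Peak, time to peak and AUC0-28 are largely settled by day 28 and are little affected. The primary endpoint is untouched. At stake are a secondary endpoint and one descriptive comparison, so this is a cheap improvement of low severity.

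**What to change.** Under Secondary endpoints and Statistical analysis of dose-response relationship:

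1. Analyse persistence as time from infusion to first negative q-PCR, censored at the last q-PCR sample for subjects still positive, and summarise it by Kaplan-Meier.
2. Relate persistence to response only from a named landmark visit: classify subjects by response status at that visit and count persistence from it.
3. Base the other responder comparisons on peak, time to peak and AUC0-28, which Metabolic kinetic endpoints already lists.

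It would also help to state whether q-PCR sampling continues after progression or withdrawal; the censored analysis works either way.

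The cost is a few lines of text and no new data. There are two statistical costs. Subjects who leave, or are already negative, before the landmark drop out of that comparison, which matters with 10 to 30 subjects. Censoring also assumes that stopping of sampling is unrelated to persistence within each group. The simulation made that assumption too, and it tested censoring but not the landmark; the landmark rests on the argument that response is known only after follow-up has begun.
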